8.4 Reporting Procedure

8.4.1 AEs and SAEs

All adverse events and serious adverse events that should be reported as defined in section 8.1.1 will be recorded in the patient's CRF.

SAEs must be reported by the investigator to the sponsor, Oslo University Hospital by contact [name], within 24 hours after the site has gained knowledge of the SAE. Every SAE must be documented by the investigator on the SAE pages (to be found in the CRF). The Serious Adverse Event Report Form must be completed, signed and sent to the Regional Ethics Committee (REK) and the Norwegian Medicine Agency (SLV). The initial report shall promptly be followed by detailed, written reports if necessary. The initial and follow-up reports shall identify the trial subjects by unique code numbers assigned to the latter.

The sponsor keeps detailed records of all SAEs reported by the investigators and performs an evaluation with respect to seriousness, causality and expectedness.

8.4.2 SUSARs

SUSARs will be reported to the Competent Authority. The following timelines should be followed:

The sponsor will ensure that all relevant information about suspected serious unexpected adverse reactions that are fatal or life-threatening is recorded and reported as soon as possible to the Competent Authority (i.e. SLV) and Ethics Committee (i.e. REK) in any case no later than seven (7) days after knowledge by the sponsor of such a case, and that relevant follow-up information is subsequently communicated within an additional eight (8) days.

All other suspected serious unexpected adverse reactions will be reported to the Competent Authority (i.e. SLV) concerned and to the Ethics Committee (i.e. REK) concerned as soon as possible but within a maximum of fifteen (15) days of first knowledge by the sponsor.

SUSARs will be reported using the CIOMS form scanned sent by e-mail.

8.4.3 Annual Safety Report

Once a year throughout the clinical trial, the sponsor will provide the Competent Authority with an annual safety report. The format will comply with national requirements.

8.4.4 Clinical Study Report

The adverse events and serious adverse events occurring during the study will be discussed in the safety evaluation part of the Clinical Study Report.

8.5 Procedures in Case of Emergency

The investigator is responsible for assuring that there are procedures and expertise available to cope with emergencies during the study.

9 DATA MANAGEMENT AND MONITORING

9.1 Case Report Forms (CRFs)

The investigator will enter the data required by the protocol into the Case report forms (CRF) kept in paper format. The PI is responsible for assuring that data entered into the CRF is complete, accurate, and that entry is performed in a timely manner. The signature of the investigator will attest the accuracy of the data on each CRF. If any assessments are omitted, the reason for such omissions will be noted on the CRFs. Corrections, with the reason for the corrections will also be recorded.

The CRF will be completed legibly in black ink, with reasons given for any missing data. Any errors should be corrected by a single line strike-through, and annotated with the current date and initials of the person correcting the error. Under no circumstances should data be permanently obliterated with ink or correcting fluid.

The PI will sign the last page of the CRF. Any corrections to the data will be made in a manner that does not obscure the original entry and will be dated and initialed by the investigator or assigned designee.

9.2 Source Data

The medical records for each included subject should contain information which is important for the patient's safety and continued care, and to fulfill the requirement that critical study data should be verifiable.

To achieve this, the medical records of each patient should clearly describe at least:

- That the patient is participating in the study, e.g. by including the enrollment number and the study code or other study identification;
- Date when Informed Consent was obtained from the patient and statement that patient received a copy of the signed and dated Informed Consent;
- Results of all assessments confirming a patient's eligibility for the study;
- Diseases (past and current; both the disease studied and others, as relevant);
- Surgical history, as relevant;
- Treatments withdrawn/withheld due to participation in the study;
- Results of assessments performed during the study;
- Treatments given, changes in treatments during the study and the time points for the changes;
- Visits to the clinic / telephone contacts during the study, including those for study purposes only;
- Non-Serious Adverse Events and Serious Adverse Events (if any) including causality assessments;
- Date of, and reason for, discontinuation from study treatment;
- Date of, and reason for, withdrawal from study;
- Date of death and cause of death, if available;

Source data will be recorded directly into the CRF in addition to the patient's medical record.

9.3 Study Monitoring

The protocol and study conductance will be reviewed by a Clinical Study Monitor, who will check the following:

- Informed consent process
- Reporting of adverse events and all other safety data
- Adherence to protocol
- Maintenance of required regulatory documents
- Study Supply accountability
- Facilities and equipment (example: laboratory, pharmacy, ECG machine, etc...)
- Data completion on the CRFs including source data verification (SDV).

The monitor will review the relevant CRFs for accuracy and completeness and will ask the site staff to adjust any discrepancies as required.

When the responsible study monitor has checked and verified the CRFs, the data will be entered into a computer database at the OUH's scientific server (i.e. K:\Forskning\Forskningsstudier) for further handling and statistical evaluation. For verification the data will be entered twice at two separate sessions.

Sponsor's representatives (e.g. monitors, auditors) and/or competent authorities will be allowed access to source data for source data verification in which case a review of those parts of the hospital records relevant to the study may be required.

9.4 Confidentiality

The investigator will arrange for the secure retention of the patient identification and the code list. Code list and signed informed consent forms will be kept in a locked cabinet at the principle investigator's office. Patient files shall be kept for the maximum period of time permitted by each hospital. The study documentation (CRFs, Site File etc.) shall be retained and stored during the study and for 15 years after study closure. All information concerning the study will be stored in a safe place inaccessible to unauthorized personnel.

9.5 Database management

All included subject will be assigned a unique study number which will be used along with initials in all further data handling. The code list will be kept in paper only and stored in a locked cabinet at the PI's office.

During the study the CRFs will be stored at the technician's office at the R&D section at Dep. of Infectious Diseases, OUH. CRFs from subjects that have completed the study will be stored in the office in an open book shelf in the PI's office at OUH.

To promote data quality, data from CRF and results from assessments will be entered doubly into two separate Excel spreadsheets at two separate sessions. The double entries will subsequently be compared and merged in order to avoid data inaccuracies resulting from data entry errors. All entries and changes in the CRF, data files or database will be logged by signature (initials) of entrant and date of entry.

Data entered electronically will be kept at the OUH's scientific server (i.e. K:\Forskning\Forskningsstudier) inaccessible for unauthorized personnel.

All data both electronically entered and in paper format, will be stored for 15 years after the last subject has completed the study. After 15 years all data will then be deleted or anonymized.

10 STATISTICAL METHODS AND DATA ANALYSIS

10.1 Determination of Sample Size

The study probiotic (IDOFORM®Travel) has previously not been tested in HIV-infected patients. Other probiotics have been well tolerated in other samples of HIV-infected patients, but has not been tested in INR patients.(58-60) We expect the probiotic to have few side effects and adverse events occurring at a low frequency. The study design for assessment of the primary objective is an uncontrolled intervention for detection of adverse events occurring at a frequency and with a severity that disqualify further efficacy studies of the investigational product.

There are no published data providing an expected frequency or variability of adverse events that could be applied in power or sample size calculations for the primary objective of this study. For the safety study, 20 patients will be observed for serious adverse events (SAE) for 8 weeks. If we observe 0/20 adverse events then we can be 95% certain that the true population proportion of SAE in 2 weeks fall within the range (0%, 17%). If we observe 1/20 adverse events then we can be 95% certain that the true population proportion of SAE in 8 weeks fall within the range (0.1%, 25%). Here the confidence intervals have been calculated using the Clopper-Pearson method.(67)

The secondary objectives of the study are exploratory. There are no relevant published data that can provide expected efficacy size or variability. Sample size calculations for the secondary objectives are therefore not feasible.

The sample size in this study is also influence by queries in our HIV database on number of patients eligible for inclusion and by available resources at the departments participating in the study.

Expert statistician at Regional Research Support at OUH has been consulted.

10.2 Population for Analysis

The following populations will be considered for the analyses:

Primary objective:

Includes all subjects who received at least one dose of the investigational product. Subjects who withdrew from the study will be included in the safety analysis. A list of withdrawn subjects, preferably with the reasons for withdrawal, will be made.

Secondary objectives:

Includes all subjects who completed biopsy sampling at the site of interest during colonoscopy.

10.3 Planned analyses

The statistical analysis is planned to be performed when all subjects have been included and completed the study treatment. No interim analyses will be made.

Deviation from the original statistical plan will be described and justified in the Clinical Study Report. Amendments to plan can be done until day of DB lock.

10.3.1 Study population variables

A table will be provided with the following information:

- number of subjects, both screened and enrolled, included in the study
- number of subjects included in the safety analysis (primary objective)
- number of subjects included in the efficacy analysis (secondary objective)
- number of subjects withdrawn from the study and the reason for withdrawal

Demographic information will be summarized using descriptive statistics.

Medical histories will be summarized by counts. Concurrent medications will be recorded and coded using a standard classification system and grouped by primary and secondary classes if applicable.

Vital signs

Categorical data will be summarized by treatment and as a total using count and percentages of patients. Continuous data will be summarized by treatment and as a total using medians, quartiles and ranges.

Physical examination

Categorical data will be summarized by treatment and as a total using count and percentages of patients. Continuous data will be summarized by treatment and as a total using median, quartiles and ranges.

Clinical Laboratory Measurements

Categorical data will be summarized by treatment and as a total using count and percentages of patients. Continuous data will be summarized by treatment and as a total using median, quartiles and ranges.

10.4 Statistical Analysis

Non-parametrical statistics will be applied for all analyses, two-sided tests only. Level of statistical significance defined as $p < 0.05$. Patients with missing values will be excluded from analysis of the parameter where value is missing. This study does not have any additional separate statistical analysis plan.

Primary endpoints: (see section 2.1)

i) Adverse events:

- a. Descriptive presentation of frequencies concurrent to study treatment. No comparative statistical analysis.

ii) Δ plasma HIV RNA load:

- a. Δ defined by changes between end of study (week 8) and baseline (week 0).
- b. Assessed by routine HIV RNA quantification at Dep. of Medical Microbiology, OUH.
- c. H_0 : Eight weeks treatment with probiotics does not change HIV RNA load in INR cART-treated chronic HIV-infected patients.
- d. Analyzed by Wilcoxon signed-rank test.

iii) Δ blood CD4 count:

- a. Δ defined by changes between end of study (week 8) and baseline (week 0).
- b. Assessed by routine CD4 cell quantification at Dep. of Immunology, OUH.
- c. H_0 : Eight weeks treatment with probiotics does not change blood CD4 cell count in INR cART-treated chronic HIV-infected patients.
- d. Analyzed by Wilcoxon signed-rank test.

Secondary endpoints: (see section 2.2)

The statistical analysis strategy is described below. As the efficacy assessments of this study are of exploratory nature, the exact parameters assessed and variable to be analyzed are difficult to predict. The conductance of the statistics may diverge from the planned analyses.

- Alterations are defined by:
 - Changes in *variable* between end of study (week 8) and baseline (week 0) in INR cART-treated chronic HIV-infected patients.

or

- Differences in *variable* between INR cART-treated chronic HIV-infected patients (week 0) (cases) and cART-treated immunological responding chronic HIV-infected patients (controls) and HIV negative subjects (healthy controls).
- Null hypothesis (H_0) will be formulated as:
 - H_{0-1} : Eight weeks treatment with probiotics does not alter the *variable* in INR cART-treated chronic HIV-infected patients.

or

- H_{0-2} : INR cART-treated chronic HIV-infected patients (week 0) (cases), cART-treated immunological responding chronic HIV-infected patients (controls) and HIV negative subjects (healthy controls) have equal *variable*.
- Statistical tests will consist of:

- Composition of microbiota tentatively analyzed by principle components analysis and Monte Carlo permutation test. Microbiota diversity tentatively analyzed by Shannon index and Simpson reciprocal index.
- For single variable analyses H₀-1s analyzed by Wilcoxon signed-rank test and H₀-2s analyzed by One-way ANOVA with Bonferroni posttests.

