4.2 Number of Patients

Twenty HIV-infected INR patients (cases) will be included in this trial. In addition, 20 HIV infected non-INR patients and 20 HIV negative individuals will be included as controls for the subsidiary cross sectional study.

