4.3 Inclusion Criteria

- 1) Subjects may be included as **cases** in the study if they meet all of the following criteria:

- HIV seropositive >4 years.
- Continuous cART >4 years.
- Plasma HIV RNA <50 copies/mL >3,5 years.¹⁾
- CD4+ T cell count <**400 cells/μL** >3.5 years.²⁾
- Male, Caucasian
- Age 25-65
- Signed informed consent and expected cooperation of the patients for the treatment and follow up must be obtained and documented according to International Committee on Harmonization (ICH) Good Clinical Practice (GCP), and national/local regulations.

2) Subjects may be included as **control** subjects in the sub-study if they meet all of the following criteria:

- HIV seropositive >4 years.
- Continuous cART >4 years.
- Plasma HIV RNA <50 copies/mL >3,5 years.¹⁾
- CD4+ T cell count >**600 cells/μL** >3.5 years.
- Male, Caucasian
- Age 25-65
- Signed informed consent and expected cooperation of the patients for the treatment and follow up must be obtained and documented according to ICH GCP, and national/local regulations.

Or if they meet all the following criteria:

- HIV seronegative.
- Male, Caucasian
- Age 25-65

Signed informed consent and expected cooperation of the patients for the treatment and follow up must be obtained and documented according to ICH GCP, and national/local regulations.

¹⁾One single measurement ("blip") of HIV RNA >50 copies/ml accepted.

²⁾One single measurement ("blip") of CD4 >400 cells/μl accepted.

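### The signed-rank test on HIV RNA does not show how many suppressed patients reach 50 copies/mL; if suppressed values are tied, which the plan leaves open, its exact form needs at least 6 same-direction rises in 20

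*Combined protocol and SAP*

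**What the plan says.** Sections 2 and 2.1 make the change in plasma viral load one of three primary endpoints, all serving the safety objective. For this endpoint section 10.4 takes the difference between week 8 and week 0, sets the null hypothesis "Eight weeks treatment with probiotics does not change HIV RNA load in INR cART-treated chronic HIV-infected patients" and prescribes: "Analyzed by Wilcoxon signed-rank test". The general rule in that section is "Non-parametrical statistics will be applied for all analyses, two-sided tests only", with significance at p < 0.05. Patients with a missing value drop out of the analysis of that parameter.

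Section 4.2 fixes the size: "Twenty HIV-infected INR patients (cases) will be included in this trial". Section 4.3 requires "Plasma HIV RNA <50 copies/mL >3,5 years", and a footnote has a single measurement "of HIV RNA >50 copies/ml accepted". It does not say that this measurement must precede week 0.

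Section 10.4 leaves measurement to the hospital's routine assay. It gives no quantification limit, no rule for results below one, no treatment of zero differences, no choice between exact and approximate test, and no category for values above the suppression limit. It also says that there is no separate analysis plan, so these points are not settled elsewhere.

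**The concern.** Everyone enters with long-standing suppression, so the safety question for this endpoint is mainly how many patients show viraemia after eight weeks of the product. A signed-rank test answers another question: whether paired differences are centred on zero. Its information comes from the non-zero differences. In this population there may be very few of those, or many that reflect only variation below 50 copies/mL. Which of the two applies depends on a reporting convention that the plan does not state.

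At stake is the reading of a primary safety endpoint. A non-significant result could stand beside several patients with detectable virus, and a significant one could arise with none. With no margin and no power stated for this endpoint, failing to reject a no-change hypothesis is not evidence of safety either.

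**Working it through.** **Inputs.** n = 20 (section 4.2); two-sided test at 0.05 (section 10.4); suppression limit 50 copies/mL with one exception allowed (section 4.3); Clopper-Pearson 95% intervals (section 10.1).

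**Step 1: the plan's own figures.** Section 10.1 gives (0%, 17%) for 0/20 and (0.1%, 25%) for 1/20. For 0/20 the Clopper-Pearson upper limit is 1 − 0.025^(1/20) = 16.8%. For 1/20 the limits are 1 − 0.975^(1/20) = 0.13% and the 97.5% quantile of Beta(2, 19) = 24.9%. Both intervals are reproduced. Neither concerns HIV RNA, for which the plan gives no precision or power.

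**Step 2: suppressed values tied.** Assume that k patients rise by distinct amounts and the other 20 − k differences are zero.

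- Exact, zeros dropped: p = 2/2^k. For k = 5, 2/32 = 0.0625; for k = 6, 2/64 = 0.03125.
- Normal approximation, zeros dropped: z = [k(k+1)/4] / √[k(k+1)(2k+1)/24]. For k = 5, 7.5/√13.75 = 2.02, p = 0.043. The continuity correction takes 0.5 off the numerator: 7.0/3.71 = 1.89, p = 0.059.
- Pratt (zeros ranked, then removed): for k = 4 the rises hold ranks 17 to 20, which sum to 74 with sum of squares 1374. Then z = 37/√(1374/4) = 37/18.53 = 2.00, p = 0.046.

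| Rises k | Exact | Normal | Normal, corrected | Pratt normal | Pratt, corrected |
|---|---|---|---|---|---|
| 3 | 0.2500 | 0.1088 | 0.1814 | 0.0835 | 0.0891 |
| 4 | 0.1250 | 0.0679 | 0.1003 | 0.0459 | 0.0489 |
| 5 | 0.0625 | 0.0431 | 0.0591 | 0.0258 | 0.0275 |
| 6 | 0.0313 | 0.0277 | 0.0360 | 0.0148 | 0.0157 |

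The smallest number of rises giving p < 0.05 is therefore 6 (exact, or corrected normal), 5 (uncorrected normal) or 4 (Pratt).

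**Step 3: what a non-significant result can contain.** The largest non-significant counts are:

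- exact: 5/20 = 25%, Clopper-Pearson 8.7% to 49.1%;
- uncorrected normal: 4/20 = 20%, 5.7% to 43.7%;
- Pratt: 3/20 = 15%, 3.2% to 37.9%.

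**Step 4: chance of reaching the exact threshold.** The documents give no expected rate of values at or above 50, so the rates here are assumptions. With X ~ Bin(20, π) and no falls, P(X ≥ 6) is 1.1% at π = 10%, 19.6% at 20%, 38.3% at 25% and 58.4% at 30%. With a threshold of 4, the chance at π = 10% is about 13%.

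**Step 5: a high value at week 0.** If one patient's permitted high value falls at week 0 and then resolves, that difference is negative. If it is the largest change, the exact test needs 11 rises (10 give p = 0.054, 11 give 0.034). If it is the smallest, 6 still suffice (p = 0.031).

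**Step 6: values below 50 reported numerically.** If all 20 pairs differ, the minimum exact p is 2/2^20 ≈ 0.000002. This can occur with every value below 50.

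**The case against.** The strongest reply is that 50 copies/mL is an eligibility threshold, not a stated quantification limit. Nothing says that lower results are recorded as equal. This stands. A reader might infer that the test cannot reach significance until six patients rebound; the documents do not support that, since step 6 shows significance with none. Even with ties, the number is 6, 5 or 4 depending on a variant that the plan does not name.

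A reader might also infer that a quarter of the patients could lose viral control unnoticed. That goes too far as well. The flow chart in section 6.1 schedules one HIV RNA sample after treatment starts, at week 8. The protocol itself treats an isolated value above 50 as compatible with suppression, so one such value does not establish loss of control.

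Nor would everything rest on the p-value. Section 8.1.1 counts abnormal laboratory findings as possible adverse events, which are reported descriptively. Section 10.3.1 promises counts for categorical and medians, quartiles and ranges for continuous laboratory data. No decision rule is tied to the signed-rank result. These points soften the problem without removing it: no HIV RNA category is defined, a median would hide a few high values, and a range shows the largest value but not how many there were.

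**Conclusion.** The concern holds in conditional form. With suppressed values tied and the exact test with zeros dropped, at least 6 of 20 patients must rise, with no falls, before p < 0.05, and 5 of 20 (25%, 8.7% to 49.1%) would be reported as non-significant. Other variants lower the threshold to 5 or 4, and a resolving week 0 value can raise it. With values below 50 reported numerically, the test responds to variation that does not cross the protocol's own limit. Either way it does not estimate how many patients are at or above 50 copies/mL.

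The thresholds assume ties, 20 complete pairs and distinct non-zero changes; the probabilities in step 4 also rest on assumed rates. That a primary analysis moves with unstated choices is itself a gap. The remedy is an added summary beside the existing endpoint; the change in viral load need not be replaced.

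**What to change.** In section 10.4, under primary endpoint ii:

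- Add, as the main safety summary of HIV RNA, the number and proportion of dosed patients with HIV RNA ≥ 50 copies/mL at week 8, with a Clopper-Pearson 95% interval, the method already used in section 10.1.
- Use patients with a week 8 value as the denominator, and state how many dosed patients have none. Section 10.2 keeps withdrawn patients in the safety population, so both figures are needed.
- Show separately any patient already ≥ 50 copies/mL at week 0, and list week 0 and week 8 values for every patient ≥ 50.
- Call these values ≥ 50 copies/mL, not rebounds, because one sample cannot separate a transient value from a sustained one.
- Keep the signed-rank p-value as descriptive. State the quantification limit, the rule for values below it, the handling of zero differences and the test variant.

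The cost is a small extra analysis and a protocol amendment. Section 10.3 allows the analysis plan to change until database lock, but section 11.3 requires prior written approval from the Competent Authority and the Ethics Committee for protocol changes that are not merely administrative. No new data are needed: HIV RNA is already measured at weeks 0 and 8.

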2 STUDY OBJECTIVES AND RELATED ENDPOINTS

The **primary objective** of this study is to assess the safety of probiotics in cART-treated INR patient with chronic HIV infection.

The **secondary objectives** are to i) explore the biological effects of probiotics in cART-treated INR patient with chronic HIV infection, and ii) investigate differences between cART-treated HIV-infected INR and non-INR patients with regards to gut microbial composition and mucosal barrier function.

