2.1 Primary Endpoint

i) Adverse effects; ii) Δ plasma viral load; and iii) Δ blood CD4 count.

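### Section 10.4 plans no confidence interval for the primary CD4 change and no reading of a non-significant test; with 20 patients, p ≥ 0.05 does not show that CD4 is preserved

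*Combined protocol and SAP*

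**What the plan says.** Section 2 gives the primary objective: it "is to assess the safety of probiotics in cART-treated INR patient with chronic HIV infection". Section 2.1 lists the endpoints under it: "i) Adverse effects; ii) Δ plasma viral load; and iii) Δ blood CD4 count". Section 4.2 sets the size of the intervention group: "Twenty HIV-infected INR patients (cases) will be included in this trial". There is no control arm (Section 3).

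For CD4, Section 10.4(iii) defines the change as week 8 against week 0 and states the null hypothesis, "Eight weeks treatment with probiotics does not change blood CD4 cell count in INR cART-treated chronic HIV-infected patients". The method line reads in full "Analyzed by Wilcoxon signed-rank test". The general rules at the head of Section 10.4 add: "Non-parametrical statistics will be applied for all analyses, two-sided tests only". They also set significance at p below 0.05 and drop a patient from the analysis of any parameter with a missing value. The same paragraph says that no separate SAP exists. Nothing in 10.4(iii) names an interval for the change, a size of fall that would matter, or how a p-value at or above 0.05 is to be read.

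Section 10.1 supports the 20 patients with Clopper-Pearson intervals for serious adverse events. It does not mention CD4, and the documents give no SD for the 8-week change.

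**The concern.** Under a safety objective the reassuring finding for CD4 is that no important fall occurred. The planned test can give evidence that CD4 changed. It cannot, by failing to reject, give evidence that CD4 did not fall. With few pairs, noisy counts or missing week 8 samples, non-significance becomes more likely whatever the true change, so imprecision pushes the result towards the one that sounds reassuring. These patients enter with CD4 below 400 cells/µL (one single higher value is allowed), so the size of fall that the data leave open is the quantity a reader needs. The plan does not provide for reporting it.

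**Working it through.** **Inputs from the documents.** n = 20 pairs, single arm; two-sided test at 0.05; change from week 0 to week 8; patients with missing values dropped, with no dropout rate given.

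**Assumption.** SD of the 8-week change in CD4: 40 to 100 cells/µL. This range is not in the documents, so results are given first in SD units.

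**Step 1: the plan's own figures.** Section 10.1 gives 95% intervals of 0% to 17% for 0/20 and 0.1% to 25% for 1/20. For 0/20 the exact upper limit is 1 − 0.025^(1/20) = 16.8%. For 1/20 the lower limit is 1 − 0.975^(1/20) = 0.13%, and the upper limit, from the beta distribution, is 24.9%. Both intervals reproduce. No counterpart is stated for CD4.

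**Step 2: power of the planned test.** The exact two-sided signed-rank test at n = 20 rejects when the smaller rank sum is 52 or less (true level 0.0484). Simulation with normal changes gives:
- true fall of 0.3 SD: 23% power
- 0.4 SD: 37%
- 0.5 SD: 54%
- 0.7 SD: 82%
- 50% power is reached at 0.48 SD and 80% at 0.68 SD.

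As a check, the paired normal approximation (1.960 + 0.842)/√20 gives 0.63 SD for 80% power, slightly optimistic at this size. With heavier-tailed changes (t with 5 degrees of freedom) the 80% point is 0.62 SD. With missing pairs and normal changes it rises to 0.72 SD at n = 18 and 0.78 SD at n = 16.

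**Step 3: width of a 95% interval.** t(0.975; 19)/√20 = 2.093/4.472 = 0.468 SD. The Hodges-Lehmann interval averaged 0.476 SD in simulation. About 0.47 SD serves for both.

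**Step 4: in cells/µL.** The chance of missing a fall is the chance that the test is not significant.

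| Assumed SD | Fall with 80% power (0.679 × SD) | 95% half-width (0.468 × SD) | Misses a mean fall of 30 | Misses a mean fall of 50 |
|---|---|---|---|---|
| 40 | 27 | 19 | 13% | about 0% |
| 50 | 34 | 23 | 30% | 1% |
| 60 | 41 | 28 | 46% | 7% |
| 75 | 51 | 35 | 62% | 21% |
| 100 | 68 | 47 | 77% | 46% |

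**Step 5: what a non-significant result can leave open.** If the estimate is just short of significance, at about −0.47 SD, the lower 95% limit is near −0.47 − 0.47 = −0.94 SD. That is about −47 cells/µL at SD 50 and −70 at SD 75.

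**Step 6: a fall confined to a few patients.** Suppose 4 of 20 have a true fall of 100 cells/µL and the other 16 have none, all with SD 50. The mean fall is 4 × 100/20 = 20, and the test flags it about 17% of the time. Individual changes would be more informative here than the group test.

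**The case against.** Several points can be made for the plan.

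A reader might infer that the plan would accept p ≥ 0.05 as proof of safety. It does not say so. Section 10.4 gives a hypothesis and a test without any decision rule, and Section 10.1 describes the design as one for detecting adverse events that would rule out further efficacy work. Safety also rests on adverse events, examination, vital signs, biochemistry and HIV RNA. This stands: the gap is the missing reading of a non-significant result, not a wrong rule.

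A reader might also infer that CD4 will not be summarised at all. Section 10.3.1 plans median, quartile and range summaries for clinical laboratory measurements. Section 6.5.1 lists CD4 counts among the laboratory tests, although Section 6.2 places them under biological markers, apart from clinical chemistry. CD4 may therefore be covered. Neither the change from baseline nor an interval for it is named.

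A third inference is that a sizeable fall would go unnoticed. That depends on an SD the documents do not give. A mean fall of 50 cells/µL would almost always be detected at SD 40 or 50, and missed in nearly half of such trials at SD 100. Section 8.1.1 also allows an abnormal laboratory finding to count as an adverse event, which could pick up a marked individual fall but not a modest shift across the group.

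Finally, a binding harm margin is hard to defend in an uncontrolled series of 20 that was not sized for CD4. With no true change, excluding a fall of M with 80% power needs n = (SD × (1.960 + 0.842)/M)². Purely for scale, M = 50 needs 8, 18 or 32 patients at SD 50, 75 or 100, and M = 25 needs 32, 71 or 126. This stands, and it is why a margin is optional below. It does not count against reporting an interval.

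**Conclusion.** The concern holds in a limited form. A primary safety endpoint is analysed only by a test of no change, without an interval for the change or a stated reading of non-significance. At n = 20 a p-value of 0.05 or more is compatible with a lower 95% limit as far down as about −0.94 SD, so it does not show that CD4 is preserved. The results in SD units assume normal changes and 20 complete pairs; the heavier-tailed check moves the 80% point only to 0.62 SD. Every figure in cells/µL rests on the assumed SD of 40 to 100. The documents do not support saying that the plan equates non-significance with safety, that no CD4 summary of any kind is planned, or that a large fall would be missed whatever the SD. The point is a cheap improvement to analysis and reporting that follows the interval reasoning Section 10.1 already uses for serious adverse events.

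**What to change.** Amend Section 10.4(iii) as follows:
- Make the primary summary the Hodges-Lehmann estimate of the change (week 8 minus week 0) with its 95% confidence interval, and state the number of complete pairs.
- Show each patient's change.
- Base the safety statement on the size of fall that the lower limit does not exclude.
- Keep the signed-rank p-value as descriptive only.

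The trial team may also set a harm margin before any week 8 result is seen. This is optional, and the choice of margin is theirs.

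The same 20 pairs are used, with no added patients, visits or samples. Because there is no separate SAP, the change is a small protocol amendment. Section 10.3 allows changes to the statistical plan until database lock, while Section 11.3 requires prior authority and ethics approval for protocol changes, so the route should be settled early. The CD4 result may then read as inconclusive. Without a control arm, neither a fall nor its absence can be attributed to the product.
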